3.5 Data Analysis and Sample Size

Data analysis: Baseline characteristics of the intervention and control groups will be compared using *t* tests and χ^2 tests or Fisher exact tests, as appropriate. Wilcoxon rank-sum tests will be used if the data does not appear to be normally distributed. These tests will be performed to also compare those who did and did not complete the follow-up assessment.

Randomization will be done using block permutation at the time of enrollment. Study staff enrolling caregivers will not be blinded to group allocation. Caregivers will not explicitly be told what group they have been assigned. Study staff will be blinded to group allocation when assessing the dose in the syringe in the picture submitted during follow-up in order to determine the primary outcome of observed dosing accuracy. Two independent study staff will assess the picture to determine the dose. Any disagreement will be adjudicated by the study PI.

The primary outcome will be the percent difference in the observed dose measured as the difference in millimeters (mL) between the dose of medication in the caregiver submitted picture during follow-up assessment compared to the prescribed dose in the electronic health record divided by the prescribed dose. For example, if the observed dose in the caregiver submitted picture was 4.5 mL and the prescribed dose in the electronic health record was 3 mL then this would be a 50% overdosing error. The observed dosing percent difference will be compared between the intervention and control groups as medians with interquartile ranges.

Last Revision: 4/21/2022

Table 4. Demographics of potentially eligible children, July 2018-June 2019 (N = 1,742)

Characteristic	N (%)
Age (y)	
0 to < 6 months	940 (54)
6 mos to <1yrs	183 (11)
12 mos to < 2 yrs	288(16)
2yrs to < 3yrs	205 (12)
3yrs to < 4 yrs	125 (7)
Sex	
Male	958 (55)
Female	784 (45)
Race/Ethnicity	
Non-Hispanic white	1098 (63)
Non-Hispanic black	244 (14)
Hispanic	296 (17)
Other	104 (6)

If we detect covariate imbalance in the two groups, we will use propensity score weighting and a multivariable linear regression model to conduct an adjusted analysis. Proposed covariates to include in the model are: caregiver health literacy, caregiver age, caregiver gender, caregiver race/ethnicity, and caregiver primary language. These covariates are likely to have the biggest impact on the primary outcome. The other covariates includes caregiver country of origin, socioeconomic status (i.e., binary outcome of do you have difficulty paying bills), employment status, education status, and marital status. Patient level covariates include child age, gender race/ethnicity, medical complexity, number of previous medications and previous hospitalizations in the last year and insurance type.

We will display our findings for the continuous outcome of observed medication dosing error using either box plots or violin plots for the intervention and control groups.

Given that prior literature in this area has examined medication dose error as a dichotomous variable using +/- 20% from the prescribed dose (this was felt to be a clinically meaningful dosing error), we will also examine and display our primary outcome in this way to allow for comparison to other studies. We will report relative risk reduction, absolute risk reduction and number needed to treat along with 95% confidence intervals for the primary outcome of both observed dosing accuracy and reported dosing accuracy.

Sample Size: Sample size estimates are based on the outcome of medication dosing accuracy. Using a conservative dosing error prevalence of 30% in the control arm,^{2,4-6,15} and an expected dosing error prevalence of 10% in the intervention arm, we will need to enroll 72 subjects in each arm of the study to reject the null hypothesis that the dosing error prevalence in the control and intervention arms are equal with 80% power (2-sided alpha of 0.05). Accounting for 25-30% loss to follow-up, we plan to enroll a total of 200 subjects. From July 2018-June 2019, the pediatric hospital medicine service at Vanderbilt discharged 1,742 children <4 years of age, at least 50% of whom were discharged home on 1 or more medications (approximately 75 children per month), ensuring ample opportunities to achieve our required sample size (see Table 4).

3.6 Potential Limitations and Alternative Approaches for Aim 1

A potential challenge is slower than anticipated enrollment. If this occurs, we will extend our enrollment period and/or consider expanding our enrollment catchment to other clinical teams or older children (e.g. school age children). Although our study is powered to detect differences similar to what has been observed in prior studies, these assumptions may be inaccurate. Nonetheless, the study would still be very useful in measuring potential effect size estimates for future study.

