Specific Aim *In a randomized controlled trial, we will test the efficacy of a health literacy-informed communication intervention on caregiver discharge medication dosing accuracy, adherence, and comprehension. We hypothesize that a useable, health literacy-informed medication counseling intervention will be efficacious in reducing liquid medication dosing errors and improve adherence and medication comprehension among caregivers following hospital discharge for children receiving liquid medication as compared to usual care.*

The primary outcome is observed dosing accuracy assessed via picture of an oral dosing syringe submitted by a caregiver 48-72 hours following discharge and compared to the prescribed dose in the chart. The primary outcome will be a continuous measure of percent difference of the caregiver submitted photo compared to the prescribed dose (in mL). The primary measure will also be assessed as a dichotomous variable as +/- 20% from the prescribed dose. Secondary outcomes include caregiver medication adherence and medication comprehension assessed via caregiver follow-up survey.

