3.4 Assessment of Outcomes

Follow-up Survey via myCap: The follow-up survey will be completed 48 to 72 hours following discharge to assess study outcomes. This will be done via myCap. myCap is an application that research participants will be asked to download on their phones (application is free and available on iPhone and Android phones). myCap leverages REDCap to capture participant/patient reported outcomes via mobile devices. myCap is HIPPA-compliant and secure. All data collected via myCap converts results into a format compatible with REDCap. The primary outcome of dosing accuracy will be assessed along with secondary outcomes (medication adherence and medication comprehension) via surveys in myCap. Caregivers will also be asked who administered the medication, what kind of teaching they received in the hospital prior to discharged (i.e., did teach-back, show-back occur), whether any serious medication errors occurred with the patient or other children in the home and/or if there were unplanned visits to a health care provider (see included follow-up survey). Caregiver self-efficacy for administering medicines to their children will be assessed using a standardized scale called the Medication Understanding and Use Self-Efficacy Scale (MUSE). See included document for RCT follow-up survey. We anticipate that the caregiver follow-up survey this will take <15 minutes to complete.

Primary Outcome: Dosing accuracy will be the primary outcome and will be assessed through self-report (reported dose) and through observation (observed dose) at follow-up. The primary outcome will be *observed dosing accuracy*. For *observed dosing accuracy*, caregivers will be asked to draw up a dose of their child's medication using the provided oral dosing syringe and send a secure picture of the syringe via myCap to research study staff (see Figure 2 as an example). The primary outcome will be assessed as a continuous percent difference from the prescribed dose (in milliliters). For *reported dose*, caregivers will be asked to report the prescribed volume (in milliliters) of medication to be given with each dose during the follow-up myCap survey. This will be compared to the prescribed dose in the electronic medical record. For both measures, dosing accuracy will also be assessed as a dichotomous outcome and considered accurate if it is within 20% of the prescribed dose similar to prior studies.^{5,15}

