Safety Monitoring Plan: If any dosing errors are detected via the myCap picture and/or myCap follow-up survey, the research team will provide additional education about proper medication dosing, refer caregivers to the prescribed dose on the medication bottle and refer the caregiver back to their child's health care provider for further questions.

Secondary Outcomes: Secondary efficacy outcomes will include discharge medication adherence and caregiver medication comprehension assessed during the myCap follow-up survey. Adherence will be calculated based on caregiver report of first and last dose of medication (compared to documentation in electronic medical record) and if there were any missed doses or if the medication was never obtained from the pharmacy. Caregiver medication comprehension will be assessed using survey questions as was done in a previous study.²⁹ We will also assess the kind of medication teaching parents received in the hospital and which aspects of the medication teaching caregivers found the most useful. Caregiver follow-up survey is included in the application. We will also collect process and exploratory outcomes as detailed in Table 3.

Table 3. Outcomes and measures obtained during myCap follow-up survey

Primary Outcome		
Outcome	Measurement definition	How measurement will be obtained
Medication Dose Accuracy	Comprehension: >20% deviation from caregiver reported dose as compared to dose in electronic health record (EHR) Adherence: >20% deviation from observed dose as compared to dose in (EHR)	Reported dose accuracy measured via caregiver self-report during post-discharge video conference call For observed dose, caregivers will be asked to measure out the prescribed volume using a syringe and submit a picture of the syringe via myCap
Secondary Outcomes		
Medication Name	Comprehension: Error in reporting medication name Adherence: N/A	Caregiver self-report during myCap follow-up survey
Medication Indication	Comprehension: Error in reporting indication for medication Adherence: N/A	Caregiver self-report during myCap follow-up survey
Medication Frequency	Comprehension: Any error in reporting frequency for medication Adherence: Any error in reporting frequency for medication	Caregiver self-report during myCap follow-up survey

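### The continuous primary outcome is signed as written, has no named test or interval, is contradicted by Table 3, and is not the outcome that the 72 per arm was sized for

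*Combined protocol and SAP*

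**What the plan says.** The Specific Aim in section 2.0 states: "The primary outcome will be a continuous measure of percent difference of the caregiver submitted photo compared to the prescribed dose (in mL"). Section 3.4 agrees: "The primary outcome will be assessed as a continuous percent difference from the prescribed dose (in milliliters"). Section 3.5 gives the formula in words, as drawn dose minus prescribed dose, divided by prescribed dose. Its one example, 4.5 mL drawn against 3 mL prescribed, ends "then this would be a 50% overdosing error".

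The planned comparison is: "The observed dosing percent difference will be compared between the intervention and control groups as medians with interquartile ranges". Display will be by "using either box plots or violin plots for the intervention and control groups". A propensity-weighted multivariable linear regression follows only if covariate imbalance is found. Wilcoxon tests appear only in the paragraph on baseline characteristics and on completers versus non-completers.

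The 20% version is introduced as an addition: "we will also examine and display our primary outcome in this way to allow for comparison to other studies". It is nevertheless the version with inference attached: relative and absolute risk reduction and "number needed to treat along with 95% confidence intervals for the primary outcome".

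Table 3, under its primary outcome heading, lists only 20% thresholds, one for reported dose and one for observed dose (">20% deviation from observed dose as compared to dose in (EHR")). The sample size paragraph compares dosing error prevalences of 30% and 10%.

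**The concern.** The trial asks whether counselling reduces dosing errors. A caregiver who draws 50% too much and one who draws 50% too little are both errors, but on a signed scale they sit on opposite sides of zero. An intervention that removed both kinds equally would leave the centre of the distribution where it was. A comparison of medians, a rank test or a linear regression on signed values therefore responds partly to the direction of error and not only to accuracy.

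The designated outcome could then show nothing while the prevalence of errors falls as assumed. With no test named, and Table 3 giving a different definition, the choice of sign and test would stay open until the data are seen. A reader would also take the 80% power as covering the primary outcome, which it does not.

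**Working it through.** **1. The plan's own figure.** Inputs from section 3.5: error prevalence 0.30 and 0.10, two-sided alpha 0.05, power 80%. With mean prevalence 0.20:

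n = [1.960 × √(2 × 0.20 × 0.80) + 0.842 × √(0.30 × 0.70 + 0.10 × 0.90)]² / 0.20² = (1.109 + 0.461)² / 0.04 = 61.6 per arm.

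With continuity correction: (61.6/4) × [1 + √(1 + 4/(61.6 × 0.20))]² = 71.2, rounded up to 72. The stated 72 reproduces, as a two-proportion sample size. For loss of 25-30%, 72/0.75 = 96 and 72/0.70 = 103 per arm, or 192 to 206 in total, so 200 is consistent. The 70-75 per arm that remain give the prevalence comparison 80-89% power, depending on the form of test.

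The documents give no standard deviation, distribution or target difference for the percent difference, so the same exercise cannot be done for it.

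**2. What the sign does.** Let s be the share of errors that are overdoses. Assume that s, the error sizes and the scatter of accurate draws are the same in both arms, and that every error lies beyond every accurate draw. Consider the probability that a control value exceeds an intervention value, ties counted half; 0.50 means no difference.

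- Control in error, intervention accurate: 0.30 × 0.90 = 0.27 of pairs.
- Control accurate, intervention in error: 0.70 × 0.10 = 0.07 of pairs.
- Both accurate or both in error: 0.63 + 0.03 = 0.66 of pairs, contributing 0.33.

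Absolute values: 0.27 + 0.33 = 0.60, whatever s is.

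Signed values: 0.27s + 0.07(1 − s) + 0.33 = 0.40 + 0.20s. This is 0.50 at an even split, 0.54 at 70/30 and 0.60 if all errors are overdoses. At an even split the signed comparison has nothing to detect.

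**3. Power, as illustration only.** Simulation at 72 per arm with prevalences 30% and 10%. Assumed: error size uniform from 20% to 100%, a rank-sum test, and accurate draws that are all exact, half exact, scattered with SD 5%, or uniform within ±20%. The ranges cover these scenarios and repeat runs.

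| Over/under split | Rank-sum power, signed values |
|---|---|
| 50/50 | 5-6% |
| 70/30 | 13-22% |
| All one way | 52-88% |

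On absolute values, power is about 53-59% when accurate draws carry noise and 86-88% when they are exact, at any split. An unadjusted linear model on signed values behaves similarly: 5% at an even split and 74-81% if all errors run one way. It is only a rough guide to the weighted model in the plan.

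**4. Medians.** Signed medians are about 0 in both arms at an even split. Even absolute medians differ little: from 0 vs 0 (exact draws) to 14.3% vs 11.1% (uniform draws), control vs intervention. Medians alone would understate a real effect on either scale.

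**The case against.** A reader might infer that the plan never says which version of the outcome leads. The documents do not support that. Sections 2.0, 3.4 and 3.5 each name the continuous measure as primary, and the 20% version is introduced as an additional look, for comparability with other studies. Table 3 may simply not have been updated. Its primary row still refers to a video call, where section 3.4 uses myCap, and it puts reported dose under the primary heading, where section 3.4 makes observed dose primary. What stands is a contradiction to reconcile, not an undecided primary outcome.

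It can also be said that absolute deviation may have been intended, since the plan speaks of accuracy and of dosing error. That is possible, but the formula and the direction-labelled example read as signed, and nothing says otherwise.

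Third, interquartile ranges and plots do show spread. At an even split the simulated control range was wider in 93-94% of trials under three of the four assumptions about accurate draws (for example 11.2 vs 7.5 percentage points with SD 5%), but in only 4% when accurate draws were all exact. This is a descriptive safeguard; no test or interval is attached to it.

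Last, the power figures rest on assumptions that the documents neither give nor exclude. That is fair: they show the direction of the problem and its possible range.

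**Conclusion.** The point holds in this form. The text designates a continuous primary outcome that, taken as written, is signed and so mixes direction with accuracy. It has no named test, effect estimate or confidence interval; Table 3 contradicts it; and the 72 per arm and 80% power belong to a binary comparison of error prevalence. That this prevalence uses the 20% cut-off is inferred from sections 3.4 and 3.5, because the sample size paragraph does not restate it. The sample size arithmetic itself is sound.

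The size of the loss cannot be fixed from the documents, because it depends on the over/under split. It ranges from nearly all power at an even split to little or none if errors run one way. A reader might go further and conclude that the 20% version should become primary because the trial was sized for it. The documents do not require that: a 20% cut discards the size of the error, and the choice is the sponsor's.

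**What to change.** 1. In sections 3.4 and 3.5, define the continuous primary outcome as |observed − prescribed| / prescribed, and use it in the group comparison and in any adjusted regression. Keep signed values for the plots and for counts of over- and underdoses.
2. Compare arms with a tie-corrected Wilcoxon rank-sum test. Beside the medians and interquartile ranges, report the probability that a control deviation exceeds an intervention deviation (ties counted half) with a 95% confidence interval.
3. Reconcile Table 3 with sections 2.0, 3.4 and 3.5. The sponsor decides which version is primary and records it in a dated amendment before arms are compared.
4. State that the 72 per arm and 80% power apply to the ±20% dosing error comparison only, and that no power is claimed for the continuous outcome.

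The photographs and data are unchanged. Recruitment was planned from July 2021 and the text was last revised on 4/21/2022, so enrolment may already have begun; hence the dated amendment. The downside is that the absolute rank-sum comparison may have less than 80% power at 72 per arm. Under the noisy-draw assumptions above, about 120-130 per arm would be needed for 80%. The plan must say that power may fall short.

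### The declared primary contrast (medians and IQRs of a percent difference with no stated sign convention) can miss the 30% versus 10% effect on which the trial was sized

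*Combined protocol and SAP*

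**What the plan says.** Section 2.0 declares the outcome: "The primary outcome will be a continuous measure of percent difference of the caregiver submitted photo compared to the prescribed dose". Section 3.5 defines it as observed minus prescribed volume, divided by the prescribed volume. Its example keeps direction. A drawn volume of 4.5 mL against 3 mL prescribed is 50% too much, and the text labels it as such: "then this would be a 50% overdosing error". Neither section says whether the analysed value is signed or absolute.

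The only between-arm comparison given for this outcome is in section 3.5: "The observed dosing percent difference will be compared between the intervention and control groups as medians with interquartile ranges". No test, effect measure or confidence interval is attached to it. Box or violin plots are planned as display, and a weighted linear regression is planned only if the arms turn out to be imbalanced on covariates.

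The same outcome is also to be dichotomised. In section 3.4 a dose is "considered accurate if it is within 20% of the prescribed dose similar to prior studies". Section 3.5 promises absolute and relative risk reductions and the NNT, with 95% CIs, for this version, and explains it as a way to set the results beside earlier studies. The sample size uses the dichotomous version only: "Using a conservative dosing error prevalence of 30% in the control arm". Set against 10% with the intervention, this gives 72 per arm.

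**The concern.** The trial is sized to find a fall from 30% to 10% in doses that are more than 20% off. That change takes place in the outer part of the distribution. A median describes the middle, and on a signed scale the quartiles may also stay in the middle, because over- and underdoses fall in opposite tails.

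The declared primary comparison could therefore show little or nothing while the dichotomous version shows a clear benefit. The plan has no rule for which of the two decides.

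**Working it through.** **Inputs.** From section 3.5: error rates 30% (control) and 10% (intervention), 72 per arm, two-sided alpha 0.05, power 80%, loss 25–30%, 200 enrolled. From section 3.4: accurate means within ±20%. The documents give no distribution of percent differences, so every shape used in steps 4 to 6 is an assumption.

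**1. The plan's own figure.** Two proportions, no continuity correction:

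n = [1.96·√(2·0.2·0.8) + 0.842·√(0.3·0.7 + 0.1·0.9)]² / 0.2² = (1.109 + 0.461)² / 0.04 ≈ 61.6, so 62.

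With continuity correction: (61.6/4)·[1 + √(1 + 4/(61.6·0.2))]² ≈ 71.3, so 72. The stated 72 is reproduced. Inflating for loss, 144/0.72 = 200, which fits the 25–30% range. The sizing is sound for the ±20% proportion.

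**2. Where the medians lie.** The shares inside ±20% are 70% and 90%. Fewer than half of the doses lie beyond either limit in either arm, so both population medians lie within ±20%. This needs no assumption about shape, sign or direction.

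**3. Sample medians.** For the median of 72 to leave the band, at least 36 of the 72 would have to be errors. The binomial probability of that is about 0.0003 at 30% and about 1e-17 at 10%.

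**4. Quartiles on the signed scale.** Suppose errors split evenly: 15% in each tail in control and 5% in each tail in intervention.
- If every accurate caregiver draws the exact volume, median [IQR] is 0 [0, 0] in both arms.
- If accurate doses are uniform on ±20%, the lower quartile is −20 + 40·(0.25 − 0.15)/0.70 = −14.3 in control and −20 + 40·(0.25 − 0.05)/0.90 = −11.1 in intervention. The summaries are 0 [−14.3, 14.3] and 0 [−11.1, 11.1].

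A signed control quartile leaves the band only if more than 25% of controls err in one direction, that is, more than 25/30 = 83% of their errors. In simulations at 72 per arm, both signed IQRs stayed inside ±20% in about 97% of trials with balanced errors and in about 78–84% with 70% overdoses. With 90% overdoses the signed control IQR stayed inside in about 33–43%. With 55% and 70% of caregivers drawing the exact volume and errors about balanced, both signed medians were exactly 0 in essentially every trial.

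**5. Quartiles on the absolute scale.** With 30% of controls beyond 20%, the control upper quartile must exceed 20%; with 10% beyond, the intervention upper quartile cannot. With in-band doses uniform and error sizes uniform from 20% to 100%, the values are 20 + 80·(0.75 − 0.70)/0.30 = 33.3 and 20·0.75/0.90 = 16.7. In samples of 72 the control upper quartile exceeded 20% in about 80% of trials.

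**6. Power at 72 per arm, 30% versus 10%, under assumed shapes.**

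| Analysis | Power |
|---|---|
| Chi-square on the ±20% outcome | 86–89% (formula 85.9%) |
| Rank-sum, signed, errors balanced | about 5% |
| Rank-sum, signed, 70% overdoses | 13–24% |
| Rank-sum, signed, all overdoses | 55–87% |
| Rank-sum, absolute | 53–88% |
| Mean absolute difference, capped at 100% | 63–82% |

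**The case against.** The strongest reply is that the trial does not depend on the medians. Section 2.0 treats the ±20% form as another assessment of the primary measure, Table 3 lists dose accuracy under the primary outcome purely as a deviation of more than 20%, and section 3.5 sizes the trial on that proportion and plans risk reductions with 95% CIs for it. This stands. A reader might infer that a real effect would go unreported; the documents do not support that. What remains is that sections 2.0, 3.4 and 3.5 name the continuous measure as primary and introduce the dichotomous one as an addition, with no rule if the two disagree.

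A second reply is that the plan reports IQRs and plots as well as medians. This also stands in part. It would be too strong to say that the problem is the same on either scale: on the absolute scale, or with strongly one-sided errors, the control upper quartile separates the arms. The insensitivity belongs mainly to a signed scale with errors in both directions, and the worked example points to a signed value without settling it.

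Third, no test is named, so no low power figure can be called the power of the planned analysis. Section 3.5 mentions the rank-sum test only for baseline and completer comparisons. If it were borrowed for the primary outcome, it would do reasonably on absolute differences and poorly on signed ones unless errors were mostly in one direction.

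Finally, medians inside the band need not be equal. With all errors overdoses and in-band doses uniform, they are −20 + 40·0.5/0.70 = 8.6% and −20 + 40·0.5/0.90 = 2.2%.

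**Conclusion.** The point holds in a limited form and should be fixed. That both medians fall inside ±20% is exact arithmetic from the plan's own rates. That the declared comparison can show no difference is a possibility and not a certainty: it needs a signed outcome and errors that are not mostly in one direction, and it is clearest when most caregivers draw the exact volume. The documents settle none of these conditions.

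The consequence is a mismatch between the declared primary contrast and the basis of the sample size, and not a trial that cannot detect its effect. The ±20% comparison has about 87% power at 72 per arm if the 30% and 10% rates are right. The other power figures depend on assumed error distributions and serve as ranges only.

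**What to change.** In section 3.5:

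- State that the ±20% risk difference with its 95% CI, which is already planned and underlies the 72 per arm, is the confirmatory comparison.
- Define the between-arm contrast for the continuous outcome on the absolute percent difference.
- Pre-specify a tail-sensitive effect estimate with a 95% CI for it, for example the difference in mean absolute percent difference with a permutation or robust interval. Fix any cap before data are seen; the choice of cap is a judgement, and the documents offer no value for it.
- Keep medians, IQRs, plots and signed values as description.

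Align the wording of the primary outcome in sections 2.0 and 3.4. Recruitment was planned from July 2021 and the document was last revised in April 2022, so the change should be dated and made before outcomes are seen by arm.

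The cost is SAP wording and a few lines of code. There are two small losses. The absolute scale drops direction, so over- and underdosing must be described separately. The continuous contrast has somewhat less power (about 63–82% under the assumed shapes, with a cap of 100%) than the ±20% proportion, which is a further reason for the proportion to carry the confirmatory claim.
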